11.4. Statistical Analysis

11.4.1. Efficacy Analysis

All confidence intervals will be two-sided 95% confidence intervals, unless stated otherwise.

11.4.1.1. Secondary Efficacy Analysis

The TE stated in this Section, include symptomatic thrombi in the systemic arterial or venous pathways (DVT, PE, stroke, SEE, intracardiac thrombus, and MI), and asymptomatic intracardiac thrombus identified by cardiac imaging.

The following secondary efficacy endpoints will be summarized by treatment group using incidence, and annualized event rate for both the Main Treatment Period and the Extension Period, as well the rate difference between edoxaban and the comparator with the corresponding 95% CI for the Main Treatment Period. The incidence of each component will also be summarized by treatment group. This analysis will be based on CEC adjudicated results.

- The combination of symptomatic TE in the systemic arterial or venous pathways including DVT, PE, stroke, SEE, intracardiac thrombus, MI, and asymptomatic intracardiac thrombus identified by cardiac imaging that occur from randomization to the Month 3 Visit.
- Deaths as a result of TE that occurs from randomization to the Month 3 Visit.
- All-cause mortality occurring from randomization to the Month 3 Visit.
- The combination of symptomatic TE in the systemic arterial or venous pathways including DVT, PE, stroke, SEE, intracardiac thrombus, and MI, and asymptomatic intracardiac thrombus identified by cardiac imaging, which occur from the day after the Month 3 Visit to the date of last dose of study drug plus 30 days for subjects who participate in the Extension Period.
- Deaths as a result of TE that occurs from the day after the Month 3 Visit to the date of last dose of study drug plus 30 days for subjects who participate in the Extension Period.
- All-cause mortality which occur from the day after the Month 3 Visit to the date of last dose of study drug plus 30 days for subjects who participate in the Extension Period.

11.4.1.2. Exploratory Efficacy Analysis

The combination of symptomatic TE and asymptomatic intracardiac thrombus, deaths as a result of TE, and all-cause mortality will also be analyzed for periods and subjects below:

- Events from randomization to the date of last dose of study drug plus 30 days for subjects who do not participate in the Extension Period
- Events from the day after the Month 3 Visit to the data of last dose of study drug for subjects who participate in the Extension Period
- Events occurring from randomization to the Month 3 Visit or to the date of last dose of study drug plus 3 days if study treatment is discontinued in the Main Treatment Period, whichever is earlier.

To assess the efficacy for intra-patient between the Main Treatment Period and previous anticoagulant regimen, TE history since diagnosis of underlying disease and within the prior 3 months to randomization will be collected. The incidence of TE and annualized event rate in the 3 months prior to randomization and during the Main Treatment Period will be calculated for subjects who have both pre-randomization and post-randomization data available. This analysis will be based on Investigator-reported events.

To compare edoxaban regimen with available existing historical control data, a literature review and a search for registered clinical trials with similar endpoints will be conducted. The available results of control data will be extracted and tabulated together with the results of the Main Treatment Period from this study.

TE will also be classified as primary prevention events and secondary prevention events based on thrombosis history, and summarized by treatment group for events occurring during the Main

Treatment Period and from the day after the Month 3 Visit to the date of last dose of study treatment plus 30 days, respectively. Due to the small sample size of the study, further stratification by primary and secondary prevention is not feasible. Hence, caution is needed in the interpretation of the result, especially when imbalance occurred between two groups.

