4. STUDY POPULATION

4.1. Inclusion Criteria

Subjects must satisfy all of the following criteria to be eligible for the study:

1. Children with cardiac diseases who are at risk for thromboembolic complications and require at least 3 months antithrombotic anticoagulant prophylaxis.

Either one of the following criteria may apply:

a. Children with cardiac disease who have a history of cardiac shunt occlusion/thrombosis, with shunt still in place (secondary prevention).

OR

b. Children with cardiac disease who require (including those already taking, and those not yet taking) anticoagulation for primary prevention of TE.

Cardiac conditions known to significantly increase the risk of thrombosis (hence, indications for primary TE prevention) are defined in Antithrombotic Therapy and Prevention of Thrombosis¹. Some examples of cardiac conditions at risk of thrombosis are Fontan surgery, heart failure, Kawasaki disease, and Blalock-Taussig and Glenn surgery.

- 2. Male or female children between 1 and <18 years of age. Children between 38 weeks gestational age and 1 year of age will be included in the study, however, only after the safety and efficacy data of 50 subjects between 1 and <18 years of age in the edoxaban arm have been evaluated at the end of the 3-month treatment period.
- 3. Subject and/or parent(s)/legal guardian(s) or legally acceptable representative is informed and provides signed consent for the child to participate in the study with edoxaban treatment. Pediatric subjects with appropriate intellectual maturity will be required to sign an assent form in addition to the signed informed consent from the parent(s)/legal guardian(s) or any legally acceptable representative.
- 4. Female subjects of childbearing potential must test negative for pregnancy at Randomization and must consent to avoid becoming pregnant by using a locally approved contraception method throughout the study. For locally approved contraceptive methods, see Appendix 17.3.
- 5. If the subject has a history of a TE that meets all of the following criteria:
 - Old, organized and/or resolved per the discretion of the Principal Investigator (confirmation of an old, organized and or resolved TE is not required by any imaging studies), and
 - The subject is asymptomatic, and
 - The subject continues to require at least 3 months of anti-coagulation treatment, and
 - There is no intracardiac thrombus or thrombi on the screening echo, and

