4.2. Exclusion Criteria

Subjects who meet any of the following criteria will be disqualified from entering the study:

- 1. Subjects with a history of the following up to randomization:
 - Symptomatic venous or arterial TE
 - Asymptomatic venous or arterial TE found by routine imaging
 - Asymptomatic intracardiac thrombosis confirmed by an echocardiogram during study screening period.

Note: Valid echocardiograms are defined here as images taken within 5 weeks prior to Randomization Visit.

- 2. Subjects with mechanical heart valves.
- 3. Subjects with active bleeding or high risk of bleeding contraindicating treatment with anticoagulant.
- 4. Subjects with a contraindication to the use of heparin (UFH or LMWH) and/or VKA (see Appendix 17.4).
- 5. Co-administration of antithrombotic therapy is contraindicated in edoxaban arm and SOC arm except for low dose aspirin defined as 1 to 5 mg/kg/day with maximum of 100 mg/day (see Appendix 17.5).
- 6. Administration of rifampin is prohibited during the study and subjects on concomitant use of rifampin are excluded (see Appendix 17.5.6).
- 7. a) Subjects with severe hepatic impairment or hepatic disease associated with coagulopathy (eg, acute hepatitis, chronic active hepatitis, and cirrhosis).

b) Subjects with ALT >5 × the upper limit of normal (ULN) or total bilirubin (TBL) >2 × ULN with direct bilirubin >20% of the total at Screening.

c) Subjects with aPTT >50 seconds or international normalized ratio [INR] >2.0 not related to anticoagulation therapy at Screening.

- 8. Subjects with estimated glomerular filtration rate (eGFR) <30% of normal for age and size (see Appendix 17.9).
- 9. Subjects with stage 2 hypertension defined as blood pressure (BP) systolic and/or diastolic confirmed >99th percentile plus 5 mmHg (see Appendix 17.10).
- 10. Subjects with thrombocytopenia (thrombocytes $<50 \times 10^9/L$).
- 11. Subjects with Fontan procedure with a history of or signs/symptoms suggestive of protein-losing enteropathy.
- 12. Subjects with a life expectancy less than the expected study duration (3 months).
- 13. Subjects who are known to be pregnant or breastfeeding.

- 14. Subjects who are not using an approved method of contraception (see Appendix 17.3).
- 15. Subjects with any condition that, as judged by the Investigator, would place the subject at increased risk of harm if he/she participated in the study including contraindicated medications identified in Appendix 17.6.

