- 16. Subject who participated in another interventional clinical study or treated with an experimental therapy with less than a 30-day wash-out period prior to the Screening Visit.
- 17. If any imaging is performed prior to randomization and results show a newly detected unorganized thrombus, these subjects are NOT eligible for the study.
- 18. Hypersensitivity to the active ingredient or to any of the excipients of any components of the trial treatment.
- 19. Patients with a history of thrombosis who are diagnosed with antiphospholipid syndrome who are triple positive (for lupus anticoagulant, anticardiolipin antibodies, and anti-beta 2-glycoprotein I antibodies.

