6.1. Note Concerning Echocardiogram

All subjects will have an echocardiogram at study screening to rule out asymptomatic thrombosis. Subjects with evidence of symptomatic venous or arterial thrombosis during study screening period are not permitted in the study. Valid echocardiograms are images taken within 5 weeks prior to Randomization Visit.

A follow-up echocardiogram will be taken at Month 3 to ascertain asymptomatic thrombosis. **IF** there is a symptomatic thrombosis prior to Month 3 which would represent a thrombotic event, it should be documented by the appropriate imaging procedure. A Month 3 echocardiogram will NO LONGER be necessary at Month 3 visit if a symptomatic event was experienced by the subject and was documented by an appropriate image.

In the Extension Period after Month 3, any symptomatic event will be documented and a recommended image captured to support the event. The Month 12 echocardiogram will be optional in all circumstances.

A Month 3 echocardiogram is optional if the subject experiences a symptomatic TE documented by an image. A reported post-Month 3 symptomatic TE should have a supporting appropriate

Proprietary and Confidential Page 71 image. If no symptomatic TE is reported during the Extension Period, the Investigator has the option to perform an echocardiogram at his/her discretion to rule out any asymptomatic TE at study discontinuation.

The Schedule of Events for this study is provided in Appendix 17.1.

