- An aPTT and INR assessment will be done for all subjects at Screening at local laboratory. Ensure that the subject qualifies with regard to the following central safety laboratory and radiology tests for exclusion criteria:

Echocardiogram. Note: Valid echocardiograms are images taken within 5 weeks prior to Randomization Visit. Note: The presence of a thrombus will disqualify the subject from the study.

Liver function assessments (ALT, AST, TBL, ALP) (central laboratory)

aPTT and INR (assessed locally)

Serum chemistry panel, serum creatinine, and eGFR (central laboratory)

Hematology (central laboratory)

Urinalysis (at central laboratory if dipstick is abnormal)

Note: Urinalysis can be done at local laboratory. Results of urinalysis performed at Screening by local laboratory may be used for qualification

• To expedite qualification and randomization for subjects living a distance from the Investigator site, the site may choose to use their local laboratory for screening eligibility labs. The sample should be split with analysis at both the central laboratory as well as the local laboratory. For the purpose of eligibility, the local laboratory results (aPTT, INR, ALT, TBL, eGFR, and platelet) will be utilized and entered into the eCRF.

If subjects are fulfilling eligibility conditions at the Screening/Qualification Visit, the Investigator has the option to randomize the subject at any time within 30 days. The Screening Visit and Randomization Visit may occur on the same day.

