6.4.4. Month 3 (Visit 5; End of Main Treatment Period) Procedures

All randomized subjects including those that have discontinued treatment prior to Month 3 will have an EOT assessment at Month 3.

Note: if there was a symptomatic thrombotic event experienced by the subject prior to Month 3 documented by the appropriate imaging, a Month 3 echocardiogram is not necessary since the subject has met an event endpoint.

The following will be performed at this visit:

• Perform physical examination (Section 9.9) including:

Vital signs (BP, heart rate, and body temperature after resting in a sitting or supine position [Note: the appropriate cuff size base on arm circumference will be used.])

Height and body weight (may be performed by an Investigator or other healthcare provider designated by the Investigator).

- Review concomitant medications
- Count unused study drug tablets/bottles/syringe and calculate compliance
- Safety review for AEs/SAEs
- Review for symptomatic endpoint events (bleeding, symptomatic TE with appropriate imaging)
- Complete the QOL Questionnaire. Note: the QOL can be filled out by EITHER a parent or the study participant. The same person should complete the QOL at Month 3.
- Take samples for the following:

LFTs (ALT, AST, TBL, and ALP)

Serum creatinine and eGFR assessment

Hematology

Urine pregnancy test (for females of childbearing potential)

- Discretionary anti-FXa level and/or aPTT measurement for subjects on SOC with heparin and INR assessment for the subjects on SOC with VKA
- At the Investigator's discretion to extend the study, dispense edoxaban study drug medication and review dosing instructions per subject/parent(s)/guardian(s)'s request.
- Perform echocardiogram to evaluate presence of asymptomatic thrombosis. Note: if there was a symptomatic event experience by the subject prior to Month 3 documented by the appropriate imaging, a Month 3 echocardiogram is not necessary since the subject has meet an event endpoint.

6.5. Extension Period (beyond Month 3 – Month 6, 9, and 12; Visits 6, 7, and 8)

At the Investigator's discretion, study treatment can be extended up to 12 months. All subjects will be offered edoxaban treatment for the duration of the Extension Period based on the Investigator's judgment of the subject's potential thrombotic burden.

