7.1. Assessments for Efficacy Endpoint(s)

The efficacy related endpoints are any TE including thrombi in the systemic arterial or venous pathways, intracardiac thrombi, DVT, PE, MI, SEE, and stroke which occurred during the study. This includes symptomatic TE and/or asymptomatic intracardiac thrombus.

Diagnosis of TE should be performed per the clinical site's existing protocol but should include at minimum 1 of the following:

- Asymptomatic intracardiac TE: The presence of an intra-luminal or mural thrombi within the cardiac chambers or surgical pathways on any cross-Sectional imaging modality. Mild laminar thickening of the internal surface of the Fontan pathway is not included. Echocardiography is the preferred modality in this setting.
- Symptomatic SEE (except stroke) which includes: retinal, upper limb and lower limb, mesenteric.
- The presence of cerebral infarction on computed tomography (CT) or magnetic resonance imagining (MRI) (performed after symptoms)
- The presence of symptomatic pulmonary embolism requires meeting 1 or more of the following criteria:

An intraluminal filling defect in segmental or more proximal branches of the pulmonary artery on multislice CT scan

A mismatched defect on a nuclear ventilation/perfusion scan compared to the prior imaging,

A non-diagnostic lung scan accompanied by documentation of new DVT by (Doppler) ultrasonography or venography.

• Symptomatic DVT requires meeting 1 of the following criteria:

A non-compressible venous segment of the peripheral veins on ultrasonography

The presence of an echogenic intra-luminal thrombus or absence of flow in the central venous system on Doppler ultrasonography

An intraluminal filling defect or venous obstruction on venography

An intraluminal filling defect or venous obstruction on CT angiography.

An intraluminal filling defect or venous obstruction on MR venography.

• Death as a result of a thromboembolic event, including pulmonary embolism. All deaths will be adjudicated by the CEC.

Diagnosis of fatal TE is based on 1 or more of the following:

- Objective diagnostic testing,
- Autopsy,
- Death which cannot be attributed to a documented cause and for which TE cannot be ruled out.

Diagnosis of symptomatic TE requires the confirmation by appropriate diagnostic imaging (see imaging criteria of TE) and at least one of the symptoms of TE in the following table:

 Table 7.1:
 Symptoms of Thrombotic Disorders

Locations	Symptoms

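### The before/after TE comparison in Section 11.4.1.2 cannot measure efficacy against prior treatment: eligibility filters only the pre-randomization window, and the size and direction of the resulting bias are unknown

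*Combined protocol and SAP*

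**What the plan says.** Section 2.1.3 lists as an exploratory objective a within-patient comparison of the Main Treatment Period with the treatment given in the preceding 3 months. Section 11.4.1.2 carries it out for efficacy: "The incidence of TE and annualized event rate in the 3 months prior to randomization and during the Main Treatment Period will be calculated", in subjects with data on both sides of randomization, using investigator-reported events. Section 11.4.3.1 plans the same table for bleeding.

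Several eligibility rules act on the earlier window:

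- Exclusion 1 in Section 4.2 covers "Subjects with a history of the following up to randomization". Its list is symptomatic TE, asymptomatic TE found by routine imaging, and silent intracardiac thrombosis on the screening echocardiogram.
- Exclusion 17 in the same section covers imaging before randomization: if "results show a newly detected unorganized thrombus, these subjects are NOT eligible for the study".
- Section 6.2 says of the screening echocardiogram: "The presence of a thrombus will disqualify the subject from the study".

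In the later window, Section 6.1 provides that "A follow-up echocardiogram will be taken at Month 3 to ascertain asymptomatic thrombosis", and Section 6.4.4 lists the procedure: "Perform echocardiogram to evaluate presence of asymptomatic thrombosis". Section 7.1 says of the TE endpoint: "This includes symptomatic TE and/or asymptomatic intracardiac thrombus".

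Other text lets earlier TEs in. Inclusion 1a in Section 4.1 admits "Children with cardiac disease who have a history of cardiac shunt occlusion/thrombosis, with shunt still in place (secondary prevention)". Inclusion 5 admits a past TE that the investigator judges old, organised or resolved, without imaging proof and without a minimum interval.

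**The concern.** A before/after contrast within one group is informative only if the same kind of event can be counted in both windows. Here, having a TE in the first window is itself a ground for not being enrolled, while a TE in the second window is an endpoint. The echocardiogram shows this most plainly. A silent thrombus on the screening image (valid if taken within 5 weeks before randomization) removes the child. The same finding at Month 3 is an event. Randomization does not repair this, because the contrast is within an arm.

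The stated comparator is a second problem. The Synopsis, Section 11.4.1.2 and Section 11.4.3.1 all name the earlier anticoagulant treatment. The sentence that defines the analysed children asks only for data before and after randomization, and Inclusion 1b admits children who have not yet started an anticoagulant. Untreated time can then be tabulated as prior treatment.

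At stake is the reading of one exploratory objective. Either arm could appear worse or better than prior treatment when nothing has changed.

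**Working it through.** **The plan's own figure.** The plan gives none for this comparison. Its only calculated planning figure is the bleeding interval in Section 11.6. That reproduces: −1.8% ± 1.96 × √(0.085 × 0.915/100 + 0.103 × 0.897/50) = −11.8% to 8.2%. It has no bearing here.

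**Inputs.** Arm sizes of 100 (edoxaban) and 50 (SOC) come from Section 11.6. The 3-month TE risk p is not given for this population; the 3.6% and 11% in Section 1.1 are per cardiac operation. I assume p = 1%, 2% and 4%, equal in both windows, so there is no true change. The number k of enrolled children with a TE in the earlier window is also not given, and I vary it. Follow-up is taken as complete, at most one TE is counted per child, and all randomised children are used.

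**Formula.** Each window gives n × 0.25 patient-years, so one event is worth 400/n per 100 patient-years. The expected later rate minus the earlier rate is 400 × (p − k/n).

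**Edoxaban arm, n = 100, expected spurious change per 100 patient-years:**

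| Earlier TEs admitted (k) | p = 1% | p = 2% | p = 4% |
|---|---|---|---|
| 0 | +4 | +8 | +16 |
| 1 | 0 | +4 | +12 |
| 2 | −4 | 0 | +8 |
| 4 | −12 | −8 | 0 |
| 6 | −20 | −16 | −8 |

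For example, with p = 2% and k = 0 the result is 400 × 0.02 = 8. The change is zero at k = n × p, that is at 1, 2 or 4 children.

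**SOC arm, n = 50.** With k = 0 the shifts are the same, but each admitted child now moves the rate by 400/50 = 8. Break-even is at 0.5, 1 or 2 children.

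**The same point as a ratio.** Let e be the chance of enrolment with a recent TE relative to without. The earlier risk among enrolled children is e × p/(1 − p + e × p). At p = 2%:

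- e = 0.5 gives 0.01/0.99 = 1.01%, so the later risk looks about twice the earlier one.
- e = 1 gives 2%, a ratio of 1.
- e = 2 gives 0.04/1.02 = 3.92%, a ratio of about 0.5.

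**The Month 3 echocardiogram.** These figures leave it out. Each silent thrombus it finds among 100 children adds 400/100 = 4 per 100 patient-years to the later window. The documents give no detection rate.

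**What the text says about k.** Exclusion 1, read literally, pushes k towards zero. Inclusions 1a and 5 raise it, with no time limit. For symptomatic thrombosis, Section 6.1 is narrower than Exclusion 1: it bars only evidence found in the screening period, so an earlier event inside the 3 months need not exclude. Inclusion 5 also requires every exclusion criterion to be satisfied, which conflicts with Exclusion 1. The documents therefore do not fix k.

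**The case against.** The strongest reply is that little depends on this table. It is exploratory and investigator-reported, no test is planned, and Section 11.6 says the study is not powered for conclusions. Section 11.7 leaves methods and definitions to the SAP, which could carry a caution. Section 11.3 already summarises medical history, prior medication and prevention type at baseline. All of this stands and limits the importance. It does not remove the problem: Section 11.4.1.2 presents the table as an assessment of efficacy, and its only caution concerns the split into primary and secondary prevention.

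A second reply is that the TE definition is assumed. Section 11.4.1.2 gives none for this table, and I have taken the one in Section 7.1. If only symptomatic TE were counted, the echocardiogram argument would fall away, but the filter on symptomatic TE history would remain.

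A third is that the numbers rest on assumed risks and full arms. That is fair. The analysed subset may be smaller, in which case each admitted child counts for more.

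A reader might also infer that the bias must make edoxaban look worse than prior treatment, because the exclusions remove nearly all earlier TEs. The documents do not support that. Inclusions 1a and 5 and the wording of Section 6.1 leave the admitted number open, and a handful of children reverses the expected sign. Counting previously untreated time could push towards apparent improvement, by an amount that cannot be sized.

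**Conclusion.** The concern holds as a limit on interpretation. The within-arm change in TE rate cannot measure efficacy against prior treatment, because eligibility acts on one window and protocol imaging adds events to the other. With no recent TE admitted, the expected spurious rise is 4, 8 or 16 per 100 patient-years at assumed 3-month risks of 1%, 2% or 4%, before any contribution from the Month 3 echocardiogram. Selection alone is neutral at 1, 2 or 4 admitted children per 100 and reverses beyond that. Neither the risk nor the admitted number is in the documents, so no direction can be claimed.

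The comparator is also mis-specified, since children with no prior anticoagulant can enter a table described as a comparison with one.

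A reader might extend the criticism to the between-arm TE comparison. That does not follow: eligibility is settled before randomization and the Month 3 echocardiogram is scheduled in both arms. Severity is minor.

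**What to change.** In Sections 11.4.1.2 and 11.4.3.1, or in the SAP:

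1. Restrict the before/after TE and bleeding tables to children who received an anticoagulant in the 3 months before randomization.
2. Show the tables by randomised arm, as the general rule in Section 11.1 implies, with the number of children in each arm who had a TE in the earlier window.
3. State that the within-arm TE change will not be interpreted as efficacy against prior treatment, and name the eligibility selection and the Month 3 echocardiogram as the reasons. Step 1 corrects the comparator but does not remove this selection.

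Separately, Exclusion 1, Inclusions 1a and 5, and Section 6.1 contradict one another on TE history and must be reconciled. Which rule should apply is for the sponsor to decide.

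The cost is a few sentences. No new data are needed, since prior anticoagulants (Section 5.5) and the 3-month TE and bleeding history (Section 6.2) are already recorded. The price is a smaller subset of unknown size and a weaker exploratory statement.
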